10.5.2.2. Handling of Partial Dates

Element	Reporting Detail
Concomitant Medications	
Partial dates for any concomitant medications recorded in the CRF will be imputed using the following convention:
 
 If the partial date is a start date, a '01' will be used for the day and 'Jan' will be used for the month If the partial date is a stop date, a '28/29/30/31' will be used for the day (dependent on the month and year) and 'Dec' will be used for the month. 
The recorded partial date will be displayed in listings.

Element	Reporting Detail
Adverse Events	
Any partial dates for adverse events will be raised to data management. If the full date cannot be ascertained, the following assumptions will be made:
 
• If the partial date is a start date, a '01' will be used for the day and 'Jan' will be used for the month.• However, if these results in a date prior to Week 1 Day 1 and the event could possibly have occurred during treatment from the partial information, then the Week 1 Day 1 date will be assumed to be the start date.• The AE will then be considered to start on-treatment (worst case).• If the partial date is a stop date, a '28/29/30/31' will be used for the day (dependent on the month and year) and 'Dec' will be used for the month. 
The recorded partial date will be displayed in listings.

10.5.2.3. Handling of Missing Data for Statistical Analysis

No missing data imputation methods will be used.

10.6. Appendix 6: Values of Potential Clinical Importance

10.6.1. Laboratory Values

Laboratory parameters have been reviewed against those specified in the protocol and any parameters not specified here have been assigned as not essential for assessment.

Haematology				
Laboratory Parameter	Units	Category	Clinical Concern Range	
			Low Flag (< x)	High Flag (>x)
Hematocrit	Ratio of 1	Male		0.54
		Female		0.54
Hemoglobin	g/L	Male		180
		Female		180
Lymphocytes	x10 ⁹ / L		0.8	
Neutrophil Count	x10 ⁹ / L		1.5	
Platelet Count	x10 ⁹ / L		100	550
White Blood Cell Count (WBC)	x10 ⁹ / L		3	20

Clinical Chemistry				
Laboratory Parameter	Units	Category	Clinical Concern Range	
			Low Flag (< x)	High Flag (>x)
Albumin	g/L		30	
BUN	mmol/L			≥ 2x ULN
Calcium	mmol/L		2	2.75
Creatinine	mmol/L			≥ 1.3x ULN
Glucose	mmol/L		3	9
Potassium	mmol/L		3	5.5
Sodium	mmol/L		130	150

Liver Function				
Test Analyte	Units	Category	Clinical Concern Range	
ALT/SGPT	U/L	High	≥ 2x ULN	
AST/SGOT	U/L	High	≥ 2x ULN	
AlkPhos	U/L	High	≥ 2x ULN	
T Bilirubin	μmol/L	High	≥ 1.5xULN	
T. Bilirubin + ALT	μmol/L U/L	High	1.5xULN T. Bilirubin + ≥ 2x ULN ALT	

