Secondary Analyses	
 Pharmacodynamic/Biomarker: RAS peptide responses: Ang II, Ang(1-7), Ang(1-5) will be analysed in a manner similar to the primary endpoint using Bayesian repeated measures mixed modelling to compare the effects of Placebo vs GSK2586881, for Part 2, if data permit. Part 1 data may also be analysed. Data from Part 1 and Part 2 will also be presented descriptively. Safety: Oxygen saturation will be analysed in a manner similar to the primary efficacy endpoint using Bayesian repeated measures mixed modelling to compare the effects of Placebo vs GSK2586881. Analyses will be performed for Part 1 and Part 2 separately. Vital signs, 12-Lead ECG, AEs and Labs will be tabulated and/or listed by treatment group, study part (Part 1 and 2) and timepoint as appropriate. Immunogenicity: Data will be tabulated and/or listed. Pharmacokinetic: Plasma concentrations of GSK2586881 and derived PK parameters will be summarised descriptively/graphically and listed for Part 1 and Part 2 of the study.
Exploratory Analyses	
 Pharmacodynamic/Biomarker: The disease biomarker Surfactant Protein D will be analysed in a manner similar to the primary efficacy endpoint using Bayesian repeated measures mixed modelling to

Overview	Key Elements of the RAP
	
compare the effects of Placebo vs GSK2586881, for Part 2, if data permit. Part 1 data may also be analysed. Data from Part 1 and Part 2 will also be presented descriptively.
 
Ventilatory parameters (Oxygen consumption (VO₂), Carbon dioxide production (CO₂), Total Tidal Volume, Inspiratory Tidal Volume, Expiratory Tidal Volume, Total Respiratory Time, Inspiratory Time, Expiratory Time, Duty Cycle, Mean Respiratory Flow and Respiratory rate) will be summarised descriptively and listed, by treatment group, timepoint and study part (Part 1 and 2).
 
Pulmonary vascular resistance (PVR) will be summarised descriptively and listed, by treatment and timepoint, for Part 2. A statistical analysis similar to that described for PASP will also be performed.
 
• Pharmacogenetics 
Analysis of pharmacogenetic data will be carried out separately by the GSK Genetics team and a separate RAP will be produced. As this is an exploratory endpoint, the results will be available separately to the CSR (or to be included as an appendix).

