2.2. Study Objective(s) and Endpoint(s)

Objectives	Endpoints
Primary Objective	Primary Endpoint

 To evaluate the effect of a single IV dose of GSK2586881 on the HPV response in healthy volunteers during exercise under hypoxic conditions 	
 Change from baseline of Pulmonary Artery Systolic Pressure (PASP) measured via Echocardiography
Secondary Objectives	Secondary Endpoints

 To evaluate the effect of a single IV dose GSK2586881 on RAS peptide responses To evaluate the safety of a single IV dose of GSK2586881 in healthy volunteers To evaluate the pharmacokinetics of a single IV dose of GSK2586881 	
 Effect of GSK2586881 on baseline levels and changes in response to hypoxia and exercise of RAS peptides (e.g. Ang II, Ang(1-7), Ang(1-5)) Vital signs (heart rate, systolic and diastolic blood pressure) Oxygen saturation 12-lead ECGs Adverse Events (AEs) Immunogenicity Clinical laboratory assessments Continuous pulse oximetry (assessed by the site) Plasma concentrations of GSK2586881 Derived pharmacokinetic parameters
Exploratory Objectives	Exploratory Endpoints

 To evaluate the effect of a single IV dose of GSK2586881 on ventilatory parameters in healthy volunteers during exercise in hypoxic conditions To evaluate the pharmacodynamic activity of a single IV dose of GSK2586881 in healthy volunteers during exercise in hypoxic conditions To evaluate the effect of a single IV dose of GSK2586881 on the HPV response in healthy volunteers under hypoxic 	
Change from baseline of:
 
 Oxygen consumption (VO₂) Carbon dioxide production (CO₂) And other parameters as data permit 
 Change from baseline in Surfactant Protein D and/or additional analytes to be determined Estimation of pulmonary vascular resistance (PVR) measured via Echocardiography

Objectives	Endpoints
conditions (and during exercise under hypoxic conditions).	

 To evaluate Pharmacogenetics 	
 Evaluate I/D polymorphisms in the Angiotensin Converting Enzyme (ACE) gene and analyse the impact on Ang II (and possibly other RAS peptides), hypoxic pulmonary vasoconstriction and responses to GSK2586881 administration

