8. SECONDARY ANALYSES

8.1. Safety Analyses

8.1.1. Overview of Planned Analyses

The safety analyses will be based on the Modified Intent-To-Treat populations (mITT, mITT1 and mITT2), unless otherwise specified.

[Table 4](#) provides an overview of the planned analyses, with further details of data displays being presented in [Appendix 11: List of Data Displays](#).

Table 4 Overview of Planned Safety Analyses

Endpoint / Parameter/ Display Type	Absolute						Change from Baseline											
	Stats Analysis			Summary			Individual			Stats Analysis			Summary			Individual		
	T	F	L	T	F	F	L	T	F	L	T	F	F	L				
Oxygen Saturation																		
Oxygen Saturation, measured by continuous pulse oximetry				Y	Y	Y	Y	Y ¹	Y		Y							
Oxygen Saturation vs PASP ²					Y													
Pulmonary Vascular Resistance																		
PVR collected via ECHO				Y	Y	Y	Y	Y ¹	Y		Y							
Adverse Events																		
All AEs for Non- randomised Subjects								Y										
All AEs by SOC and PT ³				Y				Y										
AEs Leading to Study Discontinuation								Y										
Drug-Related AEs by SOC and PT				Y														
All Serious AEs				Y			Y											
All Laboratory⁴																		
Laboratory Values of PCI								Y										
All Laboratory Data for Subjects with any Value of PCI								Y										
ECG																		
ECG Findings				Y			Y											
ECG Values by Visit				Y						Y								
ECG Values of PCI				Y			Y			Y								
All ECG Values for Subjects with any Value							Y											

Endpoint / Parameter/ Display Type	Absolute						Change from Baseline						
	Stats Analysis			Summary		Individual	Stats Analysis			Summary		Individual	
	T	F	L	T	F	F	L	T	F	L	T	F	F
of PCI													
Vital Signs													
Vital Signs by Visit				Y						Y			
Vital Signs of PCI							Y						
All Vital Signs for Subjects with any Value of PCI							Y						
Immunogenicity													
Immunogenicity				Y			Y						

NOTES :

- T = Table, F = Figure, L = Listing, Y = Yes display generated, PCI = Potential Clinical Importance
- Stats Analysis = Represents TFL related to any formal statistical analyses (i.e. modelling) conducted.
- Summary = Represents TFL related to any summaries (i.e. descriptive statistics) of the observed raw data.
- Individual = Represents FL related to any displays of individual subject observed raw data.
- 1. One table to include statistical analysis medians (95% Crl) and posterior probabilities.

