12.	All Screened Subjects	AE9CP	Listing of All Adverse Events for Non-randomised subjects	Only output AEs that occurred for non-randomised subjects only. These should be assigned as pre-treatment. If no AEs then list 'No data to report'. Any SAEs will be noted on this listing. Include footnote: Study Part 1 (subject numbers P to PPD Study Part 2 (subject numbers PPD	SAC
13.	mlITT	AE9CP	Listing of All Adverse Events	Will include AEs for mlITT patients, including those that occurred pre-treatment. Include footnote: Study Part 1 (subject numbers P to PPD Study Part 2 (subject numbers PPD	IA[1] (GSK), SAC (FSP)
Serious and Other Significant Adverse Events					
14.	mlITT	AE9CPA (same as CP_AE9a)	Listing of Serious Adverse Events	As above Include footnote: Study Part 1 (subject numbers P to PPD Study Part 2 (subject numbers PPD	SAC
15.	mlITT	AE9CP	Listing of Adverse Events Leading to Withdrawal from Study / Permanent Discontinuation of Study Treatment	Include footnote: Study Part 1 (subject numbers P to PPD Study Part 2 (subject numbers PPD	SAC

ICH : Listings					
No.	Population	IDSL / TST ID / Example Shell	Title	Programming Notes	Deliverable [Priority]
All Laboratory					
16.	mlTT	LB6	Listing of All Laboratory Data for Subjects with Any Value of Potential Clinical Concern/Potential Clinical Importance	Group by chemistry and haematology Include footnote: Study Part 1 (subject numbers P to PPD Study Part 2 (subject numbers PPD	SAC
17.	mlTT	LB6	Listing of Laboratory Values of Potential Clinical Importance	Group by chemistry and haematology Include footnote: Study Part 1 (subject numbers P to PPD Study Part 2 (subject numbers PPD	SAC
ECG					
18.	mlTT	CP_EG4	Listing of All ECG Values for Subjects with Any Value of Potential Clinical Importance	Include footnote: Study Part 1 (subject numbers P to PPD Study Part 2 (subject numbers PPD	SAC
19.	mlTT	CP_EG4	Listing of ECG Values of Potential Clinical Importance	Include footnote: Study Part 1 (subject numbers P to PPD Study Part 2 (subject numbers PPD	SAC
20.	mlTT	CP_EG6	Listing of Abnormal ECG Findings	Include footnote: Study Part 1 (subject numbers P to PPD Study Part 2 (subject numbers PPD	SAC

ICH : Listings					
No.	Population	IDSL / TST ID / Example Shell	Title	Programming Notes	Deliverable [Priority]
Vital Signs					

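### Laboratory data are output only for subjects with a flagged value, and haemoglobin and haematocrit have no low flag, so a fall in a subject with no other flag appears in no laboratory display

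*SAP*

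**What the plan says.** SAP Section 2.2 includes "Clinical laboratory assessments" among the secondary safety endpoints. The synopsis (Section 1) states that "Vital signs, 12-Lead ECG, AEs and Labs will be tabulated and/or listed by treatment group", and also by study part and timepoint as appropriate.

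Table 4 in Section 8.1.1 has two laboratory rows, "Laboratory Values of PCI" and "All Laboratory Data for Subjects with any Value of PCI". Each is marked as an individual listing, with no summary and no change from baseline. Section 10.11.12 carries them through as Listing 16, "Listing of All Laboratory Data for Subjects with Any Value of Potential Clinical Concern/Potential Clinical Importance", and Listing 17, "Listing of Laboratory Values of Potential Clinical Importance". Sections 10.11.5 and 10.11.6 contain no laboratory table or figure.

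The flag limits are in Section 10.6.1. The haemoglobin row reads "Hemoglobin g/L Male 180", where the number stands in the high column and the low column is blank. The female row is the same, and haematocrit has only a high limit of 0.54 for both sexes. The introductory sentence says that "any parameters not specified here have been assigned as not essential for assessment".

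Section 10.3.2.1 defines screening as the laboratory baseline. By Section 10.1.1.1, laboratory samples are scheduled at screening and at follow-up, 7 to 10 days after the last dose.

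**The concern.** With listings as the only laboratory output, the flag rule decides whether a subject's results are seen at all. A rule that looks only upward for haemoglobin and haematocrit cannot pick out a subject whose values drop. Followed exactly, the plan could report a stated secondary safety endpoint while omitting such a drop. If no subject had a PCI value, the report would contain no laboratory results.

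The plan also prepares for a laboratory summary that it never produces. It defines a baseline that no laboratory display uses, and Section 10.4.3 gives a rule for non-detectable laboratory values needed for summary purposes. ECG and vital signs, listed beside laboratory tests as safety endpoints, have tables of values and of change from baseline (Tables 3.24, 3.25, 3.28, 3.29 and 3.32 to 3.35), and change-from-baseline flags in Sections 10.6.2 and 10.6.3. Laboratory tests have neither.

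**Working it through.** There is no stated figure to reproduce. The check traces the displays and applies the flag rule.

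1. **Displays.** Laboratory tables in Section 10.11.5: 0. Laboratory figures in Section 10.11.6: 0. Laboratory listings in Section 10.11.12: 2. Listing 17 prints the flagged values. Listing 16 prints every laboratory value, flagged or not, for a subject with at least one flagged value.

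2. **Flag rule (Section 10.6.1).** Haemoglobin is flagged if above 180 g/L and haematocrit if above 0.54. Neither has a lower condition, and there is no criterion for change from baseline.

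3. **Rule applied to illustrative values.** From starting haemoglobin of 130, 150 and 170 g/L, falls of 10, 20, 30, 50 and 80 g/L give values from 160 down to 50 g/L. None exceeds 180, so none is flagged. Haematocrit values of 0.45, 0.36, 0.30 and 0.25 do not exceed 0.54, so none is flagged. These numbers only exercise the rule; they are not expected results.

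4. **Is the blank cell a text-extraction fault?** Probably not. Lymphocytes and neutrophils in the same table show their limits in the low column, and the same two rows have the same blanks in the superseded plan reproduced later in the file.

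5. **When is a fall printed?** Only if the same subject has some other flagged laboratory value (another analyte, or a screening haemoglobin or haematocrit above its high limit), which brings the whole record into Listing 16. Let q be the share of subjects with another flagged value. If that is independent of the fall, the share of falls in neither listing is 1 − q. The SAP gives no q, so a range is assumed:

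| q (assumed) | 1 − q |
|---|---|
| 0.05 | 0.95 |
| 0.10 | 0.90 |
| 0.20 | 0.80 |
| 0.30 | 0.70 |

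6. **Use of the baseline.** With no laboratory table and no change-from-baseline flag, no planned laboratory display uses the screening baseline of Section 10.3.2.1.

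**The case against.** The synopsis allows laboratory data to be tabulated or listed, so a listing-only plan keeps that promise. The PCI limits record a sponsor review against the protocol, several other rows are one-sided, and which direction matters clinically is a medical choice whose rationale may lie in a protocol not shown here. In a small healthy-volunteer study, summary tables are partly a matter of taste. Much of this stands: there is no formal contradiction with the synopsis, and the blank cells may be deliberate. But these listings cover only a conditional subset of subjects, so listing as planned does not report the endpoint for everyone.

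A reader might go further in four ways that the SAP does not support.

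- *That only flagged values are ever printed.* Listing 16 prints all laboratory data for any subject with one PCI value.
- *That a fall could appear nowhere in the report.* A fall reported as an adverse event would be in Listing 13 and, if it began on treatment, in Table 3.16 or 3.17. That route depends on the investigator's judgement and does not replace reporting of the endpoint.
- *That heavy blood sampling makes a fall likely.* The schedule gives 8 times × 2 periods = 16 sampling occasions, but no blood volume. Multiplying by the three sample types (RAS peptides, SP-D, PK) gives 48, which counts samples and not blood loss.
- *That the gap bears on the hypoxia results or the treatment comparison.* Haemoglobin is not scheduled near the challenges, and for completers follow-up comes after both treatments, so these data cannot separate the two.

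**Conclusion.** The point holds as a reporting gap. Laboratory output depends on a PCI flag, and haemoglobin and haematocrit cannot be flagged for a low value. A fall of any size in a subject with no other flagged value is therefore absent from every laboratory table and listing. How often that would happen cannot be read from the SAP; the 70% to 95% range rests entirely on the assumed 5% to 30% of subjects with another flag, and on independence. The finding does not depend on a fall being likely, nor on any view of what the low limit should be. It leaves the primary PASP analysis and the oxygen saturation analysis untouched. It should be corrected because a secondary safety endpoint would otherwise be reported through a filter that misses one direction of change in two collected analytes.

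**What to change.** In Appendix 11, do one or both of the following:

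- Extend the laboratory listing to all mITT subjects, with PCI values marked.
- Add to Section 10.11.5 a summary of chemistry and haematology at screening and follow-up, with change from screening, separately for Parts 1 and 2. Use a total column only, because follow-up comes after both treatments. This would also put the baseline of Section 10.3.2.1 to use.

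Either change shows every fall without needing a limit. Update the laboratory rows of Table 4 to match.

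Separately, the sponsor's medical reviewer should confirm whether the blank low-flag cells for haemoglobin and haematocrit in Section 10.6.1 are intended, and the SAP should record the answer. No limit is proposed here.

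The cost is one changed listing or one or two standard tables, with no new data collection.

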10.6.2. ECG

ECG Parameter	Units	Clinical Concern Range	
		Lower	Upper
Absolute			
Absolute QTc Interval	msec	≥ 500	
Absolute PR Interval	msec	< 110	> 220
Absolute QRS Interval	msec	< 75	> 110
Change from Baseline			
Increase from Baseline QTc	msec	> 60	

10.6.3. Vital Signs

Vital Sign Parameter (Absolute)	Units	Clinical Concern Range	
		Lower	Upper
Systolic Blood Pressure	mmHg	< 85	> 160
Diastolic Blood Pressure	mmHg	< 45	> 100
Heart Rate	bpm	< 40	> 110

Vital Sign Parameter (Change from Baseline)	Units	Clinical Concern Range			
		Decrease		Increase	
		Lower	Upper	Lower	Upper
Systolic Blood Pressure	mmHg	≥ 20	≥ 40	≥ 20	≥ 40
Diastolic Blood Pressure	mmHg	≥ 10	≥ 20	≥ 10	≥ 20
Heart Rate	bpm	≥ 15	≥ 30	≥ 15	≥ 30

10.7. Appendix 7: Biomarker Details

Biomarker Category	Analyte	Method	Lab	Matrix	Total samples expected per subject
RAS Peptides ¹ (key endpoints)	Ang II	LCMS	Q2	Blood	8
	Ang (1-5)	LCMS	Q2	Blood	8
	Ang (1-7)	LCMS	Q2	Blood	8
Disease Biomarkers	Surfactant Protein D	Elisa	GSK	Serum	8

NOTES :

- 1. These peptides will be included in the interim analysis.
- Sampling times for each period: Pre-dose (T0), End of Infusion, 15 min Post-dose (T1), 15-45 min Post-dose, 60 min post chamber entry (T2), immediately post exercise (T3), immediately post chamber exit, 30 mins post chamber exit (T4).

10.8. Appendix 8: Model Checking and Diagnostics for Statistical Analyses

Endpoint(s)	
 PASP Oxygen Saturation RAS Peptides (AngII, Ang(1-5), Ang(1-7)) Surfactant Protein D
Analysis	
 SAS PROC MCMC: Bayesian repeated measures mixed model
	
 Fixed effects will be assigned a non-informative prior of $N(0, \text{Var}=1E6)$ and may be entered as separate univariate priors or as part of a multivariate distribution (variance covariance structure with zeros for off diagonals) in model hyperpriors. The non-informative UN priors should be an inverse Wishart distribution. If the equivalent of an unstructured variance covariance matrix does not fit then an AR(1) w/Random Effect structure may be considered, with non-informative priors $\phi \sim U[-1,1]$ for the off diagonal elements and $\sigma^2 \sim \text{invGamma}(0.0001, \text{scale}=0.0001)$. Example, for N=3: $UN = \begin{pmatrix} \sigma_1^2 & \sigma_{21} & \sigma_{31} \\ \sigma_{21} & \sigma_2^2 & \sigma_{32} \\ \sigma_{31} & \sigma_{32} & \sigma_3^2 \end{pmatrix}$ $AR(1) = \begin{pmatrix} 1 & \phi & \phi^2 \\ \phi & 1 & \phi \\ \phi^2 & \phi & 1 \end{pmatrix} * \sigma^2$ 
 Appropriate SAS helper procedures (e.g. PROC TRANSREG) may be used to convert typical “long and thin” PROC MIXED input datasets into a format appropriate for repeated measures modelling in PROC MCMC (e.g. constructing sets of factors for each class level and fixing the final level to zero) Centring of continuous covariates will take place at the input dataset stage: (value_i – average) for each subject i. Examination of trace plots of samples versus the simulation number and Geweke diagnostics to assess convergence. Autocorrelation plots and lag summary table to assess the degree of autocorrelation. Monte Carlo standard errors compared to posterior standard deviations (a rule of thumb but not binding target would be <0.05). If further diagnostics required a scatterplot matrix plot of the posterior samples of each parameter. Number of burn ins, thinning, starting points, number of posterior draws to take (10,000 as a starting default) will be customised to each model and may not be possible to specify in advance but will be modified to ensure satisfactory diagnostics are produced. For robustness, where non-informative priors are used the equivalent PROC MIXED model may be fitted (no output from this would be reported) and LS Means and estimates of treatment differences compared to the results obtained from the PROC MCMC analysis. SAS code for the random and repeated statements would be: 
 random int / subject=subjid s vcorr; repeated visit / subject=subjid*ptrtgrp type=un r rcorr; Model assumptions will be applied, but appropriate adjustments may be made based on the data.

10.9. Appendix 9: Population PK and Pharmacokinetic / Pharmacodynamic (Or Biomarker) Analyses

10.9.1. Population PK Dataset File Structure

The PME compliant file structure is a space-delimited file with each row containing the following columns of information. Data from all active treatments will be included (i.e. exclude placebo).

Decision as to whether this will be required will be made following the planned interim analysis (for study Part 2 at approximately N=3 or approximately N=6).

Note that subject numbers up to and including **PP** were enrolled into Part 1 of the study. Subject numbers from **PP** onwards will be enrolled into Part 2 of the study.

Variable short name	Assessment description	Format	Unit	Valid Values / Format
C	Data Identifier	Integer	-	0
STUD	Protocol Number	Integer	-	204987
DRUG	Name of Drug	Integer	-	Maximum 10 characters (numeric or text). 2586881
SUBJ	Subject identifier in study	Integer	-	Maximum 10 characters (numeric or text). Different identifier for each subject
CENT	Study centre identifier	Integer	-	
LABL	Indicator field describing the type of assessment in that record	Integer	See footnotes	See footnotes
AMT	Dose of GSK2586881	Decimal	Mg	Amount of drug given = Total GSK2586881 dose (mg/kg)* WT For dosing events: total dose of GSK2586881 taken For concentration events: 0
INF	Infusion Time	Decimal	h	Time during which total dose infused. (Time at end of infusion – Time of start infusion)
RATE	Rate of Infusion	Decimal	Mg/h	Rate of infusion (AMT/INF)
DGRP	Treatment Identifier	Decimal	-	DGRP=0.8 for 0.8 mg/kg treatment Dose of GSK2586881 (for all events)
PART	Study Part	Integer	-	1=Part 1 or 2=Part 2
PERIOD	Study Period	Integer	-	1=Period 1 or 2=Period 2
DAY	Study day	Integer	-	Maximum 10 characters (numeric or text) N= Day N, Actual Study Day
CTIM	Clock Time of Event	HH:MM:SS	-	Clock Time of Event
DATE	Date of Record	(DD/MM/YYYY)	-	Date of Record

Variable short name	Assessment description	Format	Unit	Valid Values / Format
TRFD	Actual time relative to FIRST dose	Decimal	Hours	When LABL = 4, TIME = 0 Hours since start of first active infusion (on Day 1). For pre-dose sample, TRFD is relative to FIRST dose/infusion
TRLD	Actual time relative to LAST dose	Decimal	Hours	When LABL = 4, TIME = 0 Hours since start of LAST infusion. For pre-dose sample, TRLD is relative to previous dose prior to sample For single dose studies TRFD and TRLD are the same
TFLAG	Time Flag	Integer	-	At T0 and LABL=6, TFLAG=0 At T1 and LABL=6, TFLAG=1 At T2 and LABL=6, TFLAG=2 At T3 and LABL=6, TFLAG=3 At T4 and LABL=6, TFLAG=4 Otherwise if LABL=6, TFLAG=5 If LABL="0" or "4", TFLAG=6
DV	Dependent Variable	Decimal	pg/mL	When LABL=6, observed GSK2586881 concentration at time specified by TRLD. When LABL=4 (dosing record), DV=0
MDV	Missing Data Variable	Integer	-	Either '0' if DV value present or 1 if DV value is non-quantifiable (NQ) or LABL=4
MDV1	Missing data variable	Integer	-	Either '0' if LABL=6 or '1' if LABL=4
TYPE	F-Flag	Integer	-	If MDV1='1' then TYPE ='0', If DV value present (but not NQ) TYPE='1' If DV value NQTYPE = '2'
LLQ	Lower Limit of quantification	Integer	pg/mL	Lower limit of quantification for specific analyte SMS dataset (PCLLQ)
CMT	Compartment data item	Integer	-	DOSE event: CMT=1, specifies the compartment into which DOSE is introduced. OBSERVATION event: CMT =1, specifies compartment from which observation is obtained.
AGE	Age	Decimal	Yrs	Integer. Age in years at time of screening rounded down to give age at last birthday.
WT	Weight	Decimal	Kg	Weight in kilograms at time of screening.
HT	Height	Decimal	Cm	Height in centimetres at time of screening.
SEX	Subject gender	Integer	-	Integer. One of the following - 1 = male 2 = female
ETHN	Subject ethnicity	Integer	-	Integer. Code as CRF
RACE	Subject race	Integer	-	Integer. Code as CRF

Variable short name	Assessment description	Format	Unit	Valid Values / Format
BMI	Body mass index	Decimal	kg/m^2	body mass index calculated as weight divided by height squared
EVID	Event Identification data item	Integer	-	Flag indicating whether LABL contains dosing admin info or drug concentration data. Valid values are - 1 – each dosing record for subject 0 - for all other records

Assessments captured in the LABL variable

Label	Description	Units
4	Dosing records for 0.8 mg/Kg GSK2586881	
6	Observed concentration record for GSK2586881 at time specified by TRLD; excludes NA, IS and NR, includes non-quantifiable (NQ) data	pg/mL

